Patients will be recruited through the thoracic oncology clinics at Sidney Kimmel Comprehensive Cancer Center at Johns Hopkins (SKCCC).

Study Process

Upon meeting study inclusion and exclusion criteria, consented patients will be registered and enrolled. Each enrolled subject will be assigned a confidential identification number (IDN).

- Baseline evaluations to confirm stage I NSCLC are to be conducted within 60 days prior to start of SABR.
 1. Medical history and physical
 2. Standard of care diagnostic core biopsies. For patients with who have already have biopsy confirmation of a stage I NSCLC completed and wish to enroll on study, they may consent to have an additional study biopsy obtained prior to SABR.
 3. Standard of care peripheral blood collection
 4. Standard of care imaging work-up including CT scan of the chest with contrast performed with dual-energy acquisition
 5. Standard of care PET-CT

[See Appendix for Study Calendar and Procedures](#) and the following paragraph regarding study visits.

In order to minimize the need for research-only in-person visits, telemedicine visits may be substituted for in person clinical trial visits or portions of clinical trial visits where determined to be appropriate and where determined by the investigator not to increase the participants risks. Prior to initiating telemedicine for study visits the study team will explain to the participant, what a telemedicine visit entails and confirm that the study participant is in agreement and able to proceed with this method. Telemedicine acknowledgement will be obtained in accordance with the Guidance for Use of Telemedicine in Research. In the event telemedicine is not deemed feasible, the study visit will proceed as an in-person visit. Telemedicine visits will be conducted using HIPAA compliant method approved by the Health System and within licensing restrictions.

- Radiation treatment planning scan will be done prior to start of SABR.
- For SABR, a total of 48 Gy will be delivered over 4 consecutive work days or 50 Gy over 5 days.
- Prior to the second SABR treatment, 30ml of study whole blood will be obtained.
- Post-SABR study peripheral blood collection and post-SABR study DE-CT will be conducted in the 0-24 hours preceding the scheduled post-SABR biopsy.

- Post-SABR study biopsy will be conducted on the 5th to 7th day after completion of SABR.
- 100cc of study blood will be obtained and stored 1 month post SABR.

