2. Prior thoracic radiation in the region that will be treated by SABR.
3. Patient may not be receiving any other concurrent investigational agents or chemotherapy.
4. Patient may not be receiving or received immunotherapy.
5. Patients may not be on or use steroids within 14 days before radiation, and from the duration of radiation to the time of the post-SABR biopsies and blood samples. The following are

exceptions to this criterion: Intranasal, inhaled, topical steroids, or local steroid injections (e.g., intra articular injection).

6. Female patients who are pregnant from screening to completion of SABR

See Appendix for AJCC 8 NSCLC cancer staging and Screening Procedure Outline.

6 Drugs/ Substances/ Devices

- a. The rationale for choosing the drug and dose or for choosing the device to be used. -N/A
- b. Justification and safety information if FDA approved drugs will be administered for non-FDA approved indications or if doses or routes of administration or participant populations are changed. -N/A
- c. Justification and safety information if non-FDA approved drugs without an IND will be administered. -N/A

7 Study Statistics

a. Primary outcome variable.

Primary Objective: Examine the T-cell receptor profile changes induced in the tumor after SABR. If TCR next generation sequencing analysis of post-SABR tumor is feasible, a significant TCR profile change is defined as a multi-fold increase in the frequency of identified TCR complementarity determining region 3 (CDR3) regions present in post-SABR tumor biopsies when compared to control pre-SABR tumor biopsies.

b. Secondary outcome variables.

Secondary Objectives:

1. Evaluate candidate tumor antigens (mutation associated neo-antigens, MANAs, and tumor associated neo-antigens, TAAs) released from the tumor by SABR.
2. Describe the influx of key tumor infiltrating lymphocytes in the tumor after SABR.
3. Link tumor antigen recognition by activated post-SABR peripheral T-cells with candidate pre-treatment MANAs and TAAs primed by SABR.
4. Evaluate the relationship between dual-energy (DE) CT imaging characteristics, radiation dose, and early post-SABR pathologic outcomes after treatment with SABR.
5. Evaluate the safety of post-SABR biopsies

c. Statistical plan including sample size justification and interim data analysis.

Primary Objective:

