The primary objective is to estimate the change of T cell receptor level between pre-SABR and post-SABR. A greater increase in T cell receptor level suggests a greater biological effect. With 10 analyzable patients, the change between pre-SABR and post-SABR could have an estimation precision (half of the 2-sided 90% confidence interval) of 0.58 standard deviation (with appropriate transformation when the distribution of T cell receptor level does not follow a normal distribution).

Sample Size Justification: Approximately 35 patients with medically inoperable stage I NSCLC are treated at Johns Hopkins with SABR per year and 75 patients with medically operable stage I NSCLC treated a year. We have planned an accrual rate of 1-2 patients per month and expect enrollment to be complete within 1 years.

Secondary Objectives:

For all secondary endpoints, descriptive analysis but no formal hypothesis testing will be performed given the nature of exploratory analysis. These summaries will be computed for each evaluable patient at time-points before and after SABR. Plots will be used to show the changes in immune response over time both for each individual. For each patient, comparisons in the pre and post-SABR responses will be compared using paired t-tests (or Wilcoxon signed rank tests if appropriate) for continuous variables and McNemar's test for dichotomous or categorical variables. Associations between immune responses will be explored graphically (e.g. scatterplots, boxplots) and numerically (e.g. correlations, χ^2 tests).

Additional pictorial displays will be explored to evaluate the characteristics of iodine uptake after delivery of SABR in relation to SABR dose gradients.

- d. Early stopping rules.

For the primary objective: To minimize unnecessary intervention, we will monitor the post-SABR core biopsy failure rate by a Bayesian stopping rule. We will accrue patients to a different post-SABR biopsy time point, if the posterior probability of unsuccessful biopsies being larger than 70% is 70% or higher. We assume *a priori* that the post-SABR biopsy has an average of 50% successful biopsies, and there is about 22% chance that the unsuccessful biopsy rate is 70%. Based on such rules, we will assess the feasibility when 5 and 10 patients get biopsy, and determine post-SABR core biopsy is infeasible as inability to estimate T cell receptor level and change the timing of biopsies if none of 5, or less than 2 of 10 successful biopsies are observed.

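### The steroid restriction is not tied to the date of the pre-SABR control biopsy, so a steroid-exposed baseline could look like a post-SABR rise in absolute T-cell measures

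*Combined protocol and SAP*

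**What the plan says.** Section 7a makes the pre-SABR biopsy the comparator for the primary outcome: CDR3 regions "present in post-SABR tumor biopsies when compared to control pre-SABR tumor biopsies". Section 7c describes the quantity to be estimated as a change in T-cell receptor level and gives the direction of interest: "A greater increase in T cell receptor level suggests a greater biological effect". Section 4e lists no untreated group.

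The timing of the two samples is set in different places:

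- **Baseline (Section 4a, Study Process).** "Baseline evaluations to confirm stage I NSCLC are to be conducted within 60 days prior to start of SABR". The list beneath this includes "Standard of care diagnostic core biopsies" and the baseline blood collection. Patients who already have a tissue diagnosis are told that "they may consent to have an additional study biopsy obtained prior to SABR"; no other limit on the date is given.
- **Steroids (Section 5, exclusion 5).** "Patients may not be on or use steroids within 14 days before radiation", and then "from the duration of radiation to the time of the post-SABR biopsies and blood samples". Nasal, inhaled, topical and locally injected steroids are exempt, so the rule in effect concerns systemic use.

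The concomitant-medication paragraph in Section 4a mentions steroids only by referring back to the exclusion criteria.

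**The concern.** The primary outcome and the lymphocyte comparison (secondary objective 2) are within-patient contrasts, so a factor that acts on one sample and not the other enters the estimated change directly. Exclusion 5 keeps the post-SABR sample free of systemic steroids. The control sample has no matching protection. A patient on an oral course when the diagnostic core is taken on day -40, and off it from day -15, meets the criterion as written and contributes a steroid-exposed control paired with a steroid-free post-SABR sample.

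If steroids suppress the T-cell measure, recovery after stopping them runs in the direction that the trial reads as a SABR effect. There is no unirradiated group against which to see it. With ten pairs, each patient carries a tenth of the mean. If exposure at the control sample is not recorded, the analysis cannot look for the problem afterwards.

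**Working it through.** **1. The plan's own precision figure.** Section 7c gives 10 analyzable patients and a half-width of 0.58 SD for a 2-sided 90% interval. For a paired t interval, half-width = t(0.95; n-1)/√n = 1.833/3.162 = 0.580 SD. The figure reproduces.

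**2. The two windows.** The baseline window is days -60 to -1 (60 days). The restriction covers days -14 to -1 (14 days). Uncovered: 60 - 14 = 46 days, and 46/60 = 77%. This is a share of permitted calendar days, not of patients.

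**3. The post-SABR side.** Section 4a gives 4 or 5 treatment days and a biopsy on the 5th to 7th day after completion. The post-SABR sample therefore follows about three restricted weeks: 14 days, at least 4 treatment days, and the days up to at least the 5th day afterwards.

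**4. Size of a possible shift.** Assumptions, neither of which the documents supply: k of the 10 control samples are steroid-exposed; each exposed control is lowered by d, measured in SDs of the change; SABR does nothing. Then

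spurious mean rise = (k/10) × d = 0.1 × k × d SD.

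The last column is from a simulation of the 90% t interval (200,000 runs per row). Without exposed baselines it gives about 5%, as it should.

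| k | d | Shift (SD) | Shift / 0.58 | Chance that the 90% interval lies wholly above 0 |
|---|---|---|---|---|
| 1 | 0.5 | 0.05 | 9% | 6.5% |
| 1 | 1 | 0.10 | 17% | 7.6% |
| 2 | 1 | 0.20 | 35% | 11.7% |
| 3 | 1 | 0.30 | 52% | 17.4% |
| 3 | 2 | 0.60 | 104% | 29.8% |

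**5. Which measures this applies to.** The shift applies to absolute quantities: T-cell receptor level as worded in Section 7c, and lymphocyte density under secondary objective 2. Section 7a is worded as a frequency of CDR3 regions, and Figure 1 in Section 3.3.1 shows frequency within the total repertoire. If steroids halve every clone alike, a clone that was 2 of 100 becomes 1 of 50. It is 2% in both cases, so the apparent fold change is 1.0. A spurious rise on that scale would need selective loss of the clones that later dominate, and nothing in the documents speaks to that.

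**The case against.** **Size is unknown.** The documents give no rate of systemic steroid use at diagnosis and no effect of steroids on T-cells in the tumour. An affected patient must be on a non-exempt steroid at the biopsy and off it by day -15, which may be uncommon. This stands: the table is an illustration, and the 77% must not be read as the proportion of baselines exposed.

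**A stronger reading is tempting.** If steroids cut an absolute measure to 50% or 25% of its steroid-free value, an affected patient shows a 1/0.5 = 2-fold to 1/0.25 = 4-fold rise. A reader might infer that this would count as the multi-fold increase of Section 7a. The documents do not support that, because 7a is worded as a frequency and a proportional loss of T-cells leaves frequencies unchanged.

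**A rule may exist elsewhere.** The Screening Procedure Outline, Study Calendar and Laboratory Manual are cited but were not supplied. This stands: the gap is established only for the supplied text.

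**The restriction may serve radiation efficacy alone.** The concomitant-medication paragraph does give reduced radiation efficacy as its reason, in connection with anti-oxidants. That does not fully explain exclusion 5, which continues after radiation ends, up to the biopsies and blood samples. The protocol evidently treats steroids as relevant to those samples.

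**This is an estimation pilot.** With two exposed baselines at 1 SD, the shift is about a third of the half-width. That argues for a proportionate remedy. It does not remove the asymmetry.

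**Conclusion.** The point holds as a gap in design and recording, worth closing because it is cheap to close. As written, the plan allows a steroid-exposed control to be paired with a steroid-free post-SABR sample, and the supplied text neither prevents, records nor adjusts for it.

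For absolute measures, the shift under no SABR effect ranges from 0.05 to 0.60 SD for k = 1 to 3 and d = 0.5 to 2. The upper end is as large as the stated half-width. This rests on two assumptions: that systemic steroids lower these measures, and that one to three of the ten baselines are exposed. For relative CDR3 frequency the direction is uncertain, and no size is claimed.

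A reader might also infer that every tissue endpoint is affected in this way. Section 3.3.2 does not support that: whole exome sequencing uses pre-SABR tissue only, so it has no pre/post contrast to bias.

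**What to change.** 1. Reconcile Section 4a (baseline window) with Section 5 (exclusion 5) so that the steroid criterion also addresses the dates of the control biopsy and baseline blood draw. The investigators should set any steroid-free interval; the 14 days before radiation were not justified for this purpose.
2. Record systemic steroid use, with the same exceptions as exclusion 5, at each pre- and post-SABR sample.
3. Keep all obtained pairs in the primary estimate. Pre-specify a sensitivity analysis of the primary change and of the lymphocyte change that leaves out pairs exposed at baseline.
4. If the investigators prefer to disqualify exposed baselines, amend the replacement and accrual text at the end of Section 4. At present, replacement covers only withdrawal or a missing post-SABR biopsy, and accrual ends when 10 patients have both biopsies obtained. Neither provision deals with an invalid baseline.

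The cost of items 1 to 3 is a clarified criterion, one case report form field and one extra analysis. The sensitivity estimate will be less precise. By the formula in step 1 of the working, and in units of the SD of the change, the half-width is 1.860/√9 = 0.62 with one pair left out, 1.895/√8 = 0.67 with two, and 1.943/√7 = 0.73 with three.

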Pathologic and Immunologic Response After
Ablative Radiation in Lung Cancer

NCT03603002

6/20/2020

Date: June 20, 2020

Principal Investigator: [name] MD MPH _____

Application Number: IRB00163415

JHM IRB - eForm A – Protocol

- Use the section headings to write the JHM IRB eForm A, inserting the appropriate material in each. If a section is not applicable, leave heading in and insert N/A.
- When submitting JHM IRB eForm A (new or revised), enter the date submitted to the field at the top of JHM IRB eForm A.

SPARC: Studying the Pathologic and Immunologic Response after Ablative Radiation in Stage I Non-Small Cell Lung Cancer

[figure not shown]
1. Abstract

- a. Provide no more than a one page research abstract briefly stating the problem, the research hypothesis, and the importance of the research.

Problem: Lung cancer is the leading cause of cancer death in the United States. While stereotactic ablative radiotherapy (SABR) is delivered as standard treatment in patients with medically inoperable stage I non-small cell lung cancer (NSCLC), an alarming 30-40% of these patients still develop disease recurrence just outside of the radiation field and deadly distant metastases in their lifetime. Furthermore, since the abscopal response was reported in advanced NSCLC where a systemic cancer response was induced in areas away from the irradiated site when radiation was combined with immunotherapy, multiple clinical trials are currently investigating the role of combining these two modalities. Significantly, how SABR alone increases immunogenicity of a tumor is unknown. There is a critical need to elucidate the mechanism by which SABR alone incites the immune system to better develop future rational combinations of immunotherapy with SABR.

Hypothesis: SABR induced cell death will ultimately activate downstream cytotoxic T-cells and cause T-cell influx into the tumor to enhance immunogenic tumor cell kill. This is accomplished with SABR-induced tumor antigen—both mutation-associated neoantigen and tumor-associated antigen— release, priming of downstream cytotoxic T-cells, leading to specific T-cell clonal expansion, and resultant influx of these activated cytotoxic T-cells into the tumor and blood to enhance immune-mediated tumor cell kill.

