Significance: Herein we propose a pilot study to compare pre- and post-SABR core biopsies of stage I NSCLC tumors to identify SABR-induced immune-mediated tumor recognition based on a significant and specific expansion of T-cell clones using a novel T-cell receptor (TCR) sequencing assay. This will be coupled with (1) novel genomic analysis of candidate tumor antigens that may be released from the pre-SABR tumor and (2) functional validation assays to screen post-treatment peripheral blood T-cells for reactivity to these released candidate tumor antigens. In addition, cell-based analysis will be used to identify changes in key T-cell infiltrates into the post-SABR tumor.

Study Schema

The results of this pilot study may have the potential to translate into improved systemic outcomes for patients with NSCLC through future integrated trials of immune checkpoint blockade antibodies that specifically relieve the immunosuppression on the T-cell population found to be activated by SABR. Clarifying SABR-induced immune changes in the tumor and blood will identify pathways that may be exploited to enhance systemic immunity to kill micro-metastatic disease and mitigate relapse in the next generation of clinical trials.

Additional corollary imaging studies using dual-energy (DE) computed tomography (CT), a novel imaging modality that improves the material decomposition ability of CTs, may identify new imaging markers for post-SABR treatment response by comparing DE-CT imaging characteristics with SABR fields and pathologic response.

2. Objectives (include all primary and secondary objectives)

Primary Objective:

Examine the T-cell receptor profile changes induced in the tumor after SABR.

Secondary Objectives:

1. Evaluate candidate tumor antigens (mutation associated neo-antigens, MANAs, and tumor associated neo-antigens, TAAs) released from the tumor by SABR.
2. Describe the influx of key tumor infiltrating lymphocytes in the tumor after SABR.
3. Link tumor antigen recognition by activated post-SABR peripheral T-cells with candidate pre-treatment MANAs and TAAs primed by SABR.
4. Evaluate the relationship between dual-energy (DE) CT imaging characteristics, radiation dose, and early post-SABR pathologic outcomes after treatment with SABR.
5. Evaluate the safety of post-SABR biopsies

3. **Background** (briefly describe pre-clinical and clinical data, current experience with procedures, drug or device, and any other relevant information to justify the research)

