3.3 Current experience with procedures

3.3.1: Examine T-cell clonal expansion due to SABR using T-cell Receptor Sequencing.

RT enhances the diversity of the T-cell receptor (TCR) repertoire of intra-tumoral T-cells ¹⁸. Pre- and post-SABR TCR sequencing will be performed on formalin-fixed paraffin-embedded (FFPE) tumor biopsies and peripheral blood from stage I NSCLC patients. TCR repertoire and clonality will be compared and the peripheral dynamics of intratumoral T cell clonotypes will be assessed.

In a Johns Hopkins investigator-initiated study by Drs. [name], [name], and [name], TCR sequencing was used to assess T-cell clonal response after anti-PD-1 checkpoint blockade was delivered before resection. Preliminary data provided by [name] are shown in **Figure 1** below. TCR sequencing will be similarly be performed and analyzed on pre-and post-SABR tumor and blood samples.

[figure not shown]

Figure 1: Alterations in TCR V-beta frequency in NSCLC patients before and after neoadjuvant anti-PD-1

Frequency in the total TCR repertoire. (A) 10 most frequent clones in post-treatment tumor. Each symbol represents a unique V-beta sequence. (B) Comparison of frequency of all clones detected before and after PD-1 in a patient with response to immunotherapy. D-14: 14 days pre-resection; D-1: 1 day pre-resection.

3.3.2: Examine candidate mutation-associated neoantigens and tumor-associated antigens released by SABR

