- On follow-up visits, 120cc of study blood will be obtained and stored on months 3, 6, and 12 months. At the 9 month visit, 20cc of study blood will be obtained.

See Laboratory Manual, and Imaging Manual for details of the procedures.

Treatment Plan

SABR is prescribed a total dose of 48 Gy in 4 daily treatment fractions (preferred) or 50 Gy in 5 fractions (if needed per radiation oncologist's discretion). These are both standard of care SABR doses. The radiation treatment planning, prescription radiation dose, and administration will be determined by the attending radiation oncologist.

Tissue heterogeneity correction should be applied for planning. Daily on-board imaging using 3-dimensional cone beam CT (CBCT) is required before each fraction for stereotactic delivery. Additional 4-dimensional cone beam CT should be taken to verify the tumor coverage before each treatment.

General Concomitant Medication and Supportive Care Guidelines

Given a potential for interaction of high doses of anti-oxidants reducing the efficacy of radiation, the patient should abstain from the concurrent use of high dose over-the-counter vitamins, other alternative therapies, and steroids per the exclusion criteria.

Toxicity Assessments

Safety will be monitored continuously by the study investigators for the enrolled patients until study closure. All toxicities will be graded according to the Common Terminology Criteria for Adverse Events (CTCAE Version 5.0). Refer to CTCAE version 5.0 at

https://ctep.cancer.gov/protocoldevelopment/electronic_applications/docs/CTCAE_v5_Quick_Reference_5x7.pdf

- b. Study duration and number of study visits required of research participants.

Duration of Follow Up

Patients will be required to return for follow-up visits as per study calendar after SABR treatment. Patients will have completed the study on the day of the 1-year follow-up. They will not require additional follow-up on study, but should continue routine follow-up with treating provider.

- c. Blinding, including justification for blinding or not blinding the trial, if applicable.
N/A
- d. Justification of why participants will not receive routine care or will have current therapy stopped.

Duration of Therapy

In the absence of treatment delays due to adverse events, treatment may continue until one of the following criteria applies:

1. Disease progression prior to SABR,

2. Intercurrent illness that prevents further administration of treatment,

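### Section 7a's rule for a significant TCR change makes no allowance for sampling error, so an unchanged tumour can meet it, while 7c estimates a different, undefined variable

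*Combined protocol and SAP*

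**What the plan says.** Section 7a (Primary outcome variable), on condition that sequencing of the post-SABR tumour is feasible, defines a significant TCR profile change as "a multi-fold increase in the frequency of identified TCR complementarity determining region 3 (CDR3) regions present in post-SABR tumor biopsies", with the pre-SABR biopsy as comparator. It does not say how large multi-fold is, how many clones must rise, what minimum count applies, how a clone absent before SABR is treated, how unequal depth is handled, or what becomes of falls.

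Section 7c describes the primary objective as estimating the change in a T cell receptor level, with 10 analysable patients and a two-sided 90% interval of half-width 0.58 SD. That variable is not defined or tied to CDR3 frequency. Section 7d relies on the same term: a post-SABR biopsy is judged infeasible when the level cannot be estimated.

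Section 3.3.1 offers further candidates. It says "TCR repertoire and clonality will be compared", and its Figure 1 legend, from an earlier anti-PD-1 study, shows the 10 most frequent post-treatment clones (panel A) and all clones (panel B). None is named as primary. For procedures, section 4a says "See Laboratory Manual, and Imaging Manual for details of the procedures"; that manual is not among the documents.

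**The concern.** The Abstract sets out to "identify SABR-induced immune-mediated tumor recognition based on a significant and specific expansion of T-cell clones". There is no untreated comparison group, so the pre/post biopsy contrast carries that inference. A rule that looks only at clones seen afterwards, counts only increases and ignores sampling error can report expansion where nothing has changed.

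Falls are plausible on the protocol's own background. Section 3.3.1 states that "RT enhances the diversity of the T-cell receptor (TCR) repertoire of intra-tumoral T-cells", and section 3.2.3 notes that ablative doses can impair T-cell influx. Depth may also differ between the two biopsies. The hypothesis expects "resultant influx of these activated cytotoxic T-cells into the tumor and blood", which could raise the post-SABR yield, while section 3.2.3 points the other way. The direction is unknown.

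**Working it through.** **1. The plan's own figure.** Inputs from 7c: n = 10 pairs, two-sided 90% interval. Half-width = t(0.95, 9 df)/√10 = 1.833/3.162 = 0.580 SD. The stated 0.58 is reproduced. It does not depend on the rule in 7a.

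**2. One clone by hand (illustrative).** Let a clone hold 1 in 1,000 of an unchanged repertoire, with 1,000 templates read from each biopsy. The expected count is 1 each time. The chance that it is unseen beforehand is e⁻¹ = 0.37, whatever the post-SABR count, and its fold change is then undefined. If it goes from 1 template to 4, that is a 4-fold rise. Given 5 templates in all and equal depth, P(4 or more fall post-SABR) = (5 + 1)/2⁵ = 0.19, which is unremarkable.

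**3. Whole repertoire, unchanged tumour.** Assumed, since the documents give no yields: a well-mixed tumour with both biopsies drawn multinomially from one clone distribution (clones/power-law exponent 500/1.0, 2,000/0.7, 5,000/1.0, 2,000/1.5). The table gives the share of clones rising or falling at least 2-fold in frequency. The left result column takes all clones seen post-SABR; the right takes only those also seen pre-SABR.

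| Depth | Absent-pre counted as rises: up vs down | Absent-pre dropped: up vs down |
|---|---|---|
| Equal, 300-5,000 templates | 25-80% vs 4-19% | 16-24% vs 16-24% |
| Post 4-5 times deeper | 49-88% vs 7-21% | 2-6% vs 37-73% |
| Post 5 times shallower | 40-87% vs 1-5% | mirror image of the row above: rises dominate |

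The mirror image holds because, among clones seen in both samples, swapping pre and post swaps rises and falls.

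A stricter fold does not cure the left column: at 5-fold and equal depth it is 9-76% vs 0.1-1.6%. Near saturation the imbalance goes (500 clones, 20,000 templates: 6.8% vs 6.8%). The other three repertoires at 20,000 templates still give 16-50% vs 10-15%.

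**4. If only the 10 largest post-SABR clones count.** The proportion of unchanged tumours with at least one such clone rising 3-fold or more is 65-100% at 300 templates each, 5-54% at 1,000 and 0% at 5,000.

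**5. If 7c's variable were a mean log fold change over post-present clones** (0.5 added to counts), the geometric-mean fold in an unchanged tumour would be 1.1-2.5 at equal depth, 2.1-7.1 with the post sample 5 times shallower, and 0.63-0.81 with it 4-5 times deeper. The true value is 1.

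**6. Candidate remedies, same null.** Down-sampling to equal depth and selecting on pooled count of at least 10 balances the two directions: 0.15-18.4 rises vs 0.16-18.5 falls per patient. It does not stop false calls. At 1,000-5,000 templates each, about 79-100% of unchanged tumours still show at least one 2-fold riser (70-100% in a repeat simulation; the low end comes from the most skewed repertoire at 1,000 templates).

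The alternative is an exact test. Given pooled count K and depths m₁ (pre) and m₂ (post), an unchanged clone's post count is Binomial(K, m₂/(m₁ + m₂)). With Bonferroni correction across clones, at least one false expansion occurs in 0-1.3% of unchanged tumours, and in 0-1.8% under a second set of assumed repertoires (300 or 1,000 clones).

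**The case against.** The strongest reply is that the harm is indirect. The label in 7a feeds no test, decision or stopping rule; the primary analysis in 7c is estimation in a 10-patient pilot. That stands, and it limits the point. It does not remove it, because 7c's variable is undefined and 7a is the only definition of the primary outcome.

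Second, the marked excess of rises at equal depth depends on counting absent-pre clones as rises, which 7a does not say. This also stands. A reader might infer that the rule always favours expansion; the middle row of the table shows that it need not. What remains is that an unstated zero-count rule and an unknown depth ratio decide the direction.

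Third, section 3.3.1 says the sequencing will be analysed as in the earlier study, whose panel A follows the top 10 clones. On that reading the problem is negligible at 5,000 templates but not at 1,000 or fewer, and 7a states no such restriction.

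Fourth, the Laboratory Manual may hold count or input rules, so one cannot conclude that none exist. But 7a does not refer to it.

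Finally, the plan adds "functional validation assays to screen post-treatment peripheral blood T-cells for reactivity to these released candidate tumor antigens". These are further evidence, but they do not take sampling noise out of the biopsy comparison.

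**Conclusion.** The point holds in a limited form and should be fixed. As worded, 7a can label an unchanged tumour significantly changed through sampling error, and 7a, 7c and 7d do not share a defined variable. Every percentage rests on assumed repertoires and template yields. The imbalance is small near saturation, and the false signal is small if only the largest clones count at high depth.

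Two stronger readings are not supported. One is that the primary estimate or its precision is wrong: 0.58 SD is correct, and 7c is biased only if its variable is built from clones selected on the post-SABR sample, which the documents do not say. The other is that symmetric selection or down-sampling by itself would prevent false expansion calls; step 6 shows that it balances rises against falls and no more.

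**What to change.** 1. Define one per-patient variable in 7a, use it in 7c with the planned paired 90% interval, and refer to it in 7d.
2. Call a clone expanded only if it passes both a stated fold threshold and the exact test conditional on its pooled count and the two depths, with Bonferroni or false-discovery-rate control across clones. This handles zero counts and unequal depth. Apply the same two-sided rule to contractions.
3. Report contracted beside expanded clones, and lost beside newly detected clones after down-sampling to equal depth.
4. Build any net or mean summary on clones selected by pooled count at matched depth, with a stated minimum depth below which the pair is not estimable.
5. State the chosen summary's blind spot. In simulation after down-sampling, when new clones formed 30% of the post-SABR repertoire, pooled top-10 mean log fold and clonality detected this in 0% of trials and the net expanded-minus-contracted count in 0-8%. Newly detected minus lost clones detected it in 100% of trials in 19 of 20 settings and 0% in the other.

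The cost is a few lines in 7a, 7c and 7d and an added bioinformatics step; no extra patients or biopsies. Fewer clones will be called expanded, and power for rare clones is low. For example, with 500 clones tested the two-sided Bonferroni limit is 0.05/500 = 0.0001. At equal depth a clone absent beforehand has p = 2 × 0.5ᵏ, so 14 templates (0.00012) fail and 15 (0.00006) pass. Down-sampling discards templates and hides any rise in T-cell number, so raw template yield should be reported separately. The test's 0-1.3% assumes a well-mixed tumour; variation between cores would add to it and should be named as a limitation.
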